1.0 BACKGROUND AND RATIONALE

1.1 Disease Background

Leiomyomata are the most common tumors of the uterus. Though the majority of women with fibroids are asymptomatic, a significant portion suffer symptoms including abnormal bleeding, pain, pressure and abdominal distention (1). Submucosal and large intramural fibroids have also been shown to impair fertility. Many women seek treatment for fibroids but desire to retain their uterus, whether to preserve future fertility or for other personal reasons. Myomectomy is a curative treatment that allows for uterine preservation but can come at the risk of substantial intraoperative blood loss.

Studies have assessed the utility of GnRH, vasopressin, peri-cervical tourniquet, misoprostol and oxytocin, among others, in reducing intraoperative blood loss (2). Findings from small randomized trials demonstrate significantly lower intraoperative blood loss among women who receive preoperative misoprostol compared to those who receive placebo (4, 6, 7). Other research fails to demonstrate a difference in blood loss following preoperative misoprostol (8) and cites methodologic flaws with existing studies (5). Additionally, no randomized controlled trial has been done in a U.S. population. A double-blinded, randomized, placebo-controlled trial at a tertiary care center in a major U.S. city is an ideal setting for evaluation of this research question.

The aim of this study is to assess the impact of preoperative buccal misoprostol on intraoperative blood loss and clinical outcomes related to blood loss (blood transfusion, protracted hospital stay). Defining the relationship between misoprostol and blood loss during myomectomy would provide insight into the mechanism of uterine contraction and hemostasis and inform optimal preoperative clinical management of patients undergoing this common and potentially morbid procedure.

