1.4 Rationale

Abdominal myomectomy is a common procedure that comes with risks of significant morbidity, including intraoperative blood loss at time of abdominal myomectomy as well as numerous postoperative complications including an up to 20% requirement for transfusion and 2% reported conversion to hysterectomy. The significant morbidity associated with this procedure has led to studies evaluating multiple interventions to reducing bleeding during myomectomy. A systematic review of the interventions to reduce blood loss at time of myomectomy found significant reductions in blood loss with use of vaginal misoprostol however included only one randomized controlled trial (2). Since this time, other studies have been done that reproduce these findings (6, 7), though sample size in these trials is small and results are inconsistent (8). This study would augment existing data by employing a larger sample size and double-blinded design in a U.S. population. This study would also assess the impact of a route of misoprostol administration that is less invasive for patients (buccal instead of vaginal or rectal) but offers a similar pharmacokinetic profile. Outcomes assessed include estimated blood loss, need for transfusion, prolonged hospitalization, change in postoperative hemoglobin level from preoperative baseline.

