2.2 Secondary Objectives

2.2.1 To determine the effect of 400mcg buccal misoprostol at least one hour pre-procedure on the need for blood transfusion during or in post-operative course for either an abdominal or laparoscopic myomectomy

2.2.2 To determine the effect of 400mcg buccal misoprostol at least one hour pre-procedure on post-operative fever after either an abdominal or laparoscopic myomectomy.

2.2.3 To determine the incidence of adverse effects, if any, of 400mcg buccal misoprostol at least one hour prior to either an abdominal or laparoscopic myomectomy.

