2.3 Exploratory Objectives n/a**2.4 Endpoints**

Estimated blood loss as determined by anesthesia and surgeon at time of abdominal or laparoscopic myomectomy, difference between post-operative and pre-operative hemoglobin, post-operative temperature, and overall length of hospital admission.

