4.2 Toxicities and Dosing Delays/Dose Modifications

Given this is a one-time dosing, toxicities will be limited to the immediate intervention period. Any patient who receives treatment on this protocol will be evaluable for toxicity for the entire duration of action of this

medication.

According to published research, serum levels of misoprostol nadir 6 hours following administration and the duration of pharmacologic action is considered to be only 3 hours (3,5). All patients are hospitalized following abdominal myomectomy and laparoscopic such that all patients will be monitored as inpatients for a minimum of 4 hours post-operatively.

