4.6 Duration of Follow Up

Patients will be followed for the duration of their hospital admission following abdominal or laparoscopic myomectomy. Patients will be required to stay a minimum of 4 hours post-surgery. Blood will be drawn right before patient leaves the hospital, post operatively.

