10.3 Data Analyses Plans

To determine whether women who take a pre-operative dose of misoprostol experience lower blood loss during abdominal myomectomy compared to matched controls who take placebo, we will perform linear regression. We will use this model to assess for the role of numerous covariates, including gravidity, parity and age. Secondary outcomes of percent hemoglobin drop, duration of procedure and length of inpatient hospitalization will be assessed using the T test and further evaluated with multivariate-adjusted linear regression where appropriate. The need for post-operative blood transfusion between groups will be assessed with the Chi-square (Fischer's exact) test. The role of numerous potential covariates will be assessed with Chi-square (Fischer's exact) test for dichotomous variables and T test for continuous variables with $p < 0.05$.

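### Section 10.3 tests only post-operative transfusion although objective 2.2.1 also covers transfusion during surgery, and no rule covers hemoglobin drawn after a transfusion

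*Combined protocol and SAP*

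**What the plan says.** **Transfusion.** Section 2.2 (objective 2.2.1) sets out to study "the need for blood transfusion during or in post-operative course". Section 1.1 lists "clinical outcomes related to blood loss (blood transfusion, protracted hospital stay") as part of the aim, and Section 1.4 says "Outcomes assessed include estimated blood loss, need for transfusion, prolonged hospitalization, change in postoperative hemoglobin level from preoperative baseline". Neither of these two places limits the time window. Section 10.3 then gives the one analysis that names transfusion: "The need for post-operative blood transfusion between groups will be assessed", by a chi-square or Fisher's exact test.

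The endpoints in 2.4 do not mention transfusion. After blood loss they list only "difference between post-operative and pre-operative hemoglobin, post-operative temperature, and overall length of hospital admission". The outcome rows visible in 10.1 have no transfusion variable either.

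**Hemoglobin.** Section 10.1 defines percent drop as (post-operative minus pre-operative) divided by pre-operative hemoglobin. Section 10.3 assigns it a t test, followed by adjusted linear regression where appropriate. On the draw, Section 4.6 says "Blood will be drawn right before patient leaves the hospital, post operatively". No section says how a transfused woman's value is to be used, and neither transfusion nor pre-operative hemoglobin is among the covariates in 10.1.

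**The concern.** The objective and its test have different time windows. A woman who is transfused in surgery and needs nothing afterwards is an event under 2.2.1 and a non-event under the literal wording of 10.3. On that reading the test does not match the objective. If the wording stays open, the definition could also be settled after the counts are known.

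The hemoglobin problem is linked. A transfusion raises hemoglobin, so a value taken afterwards understates the fall that bleeding caused. If one arm is transfused more often, or gains more hemoglobin per transfused woman, its mean drop is masked more and the comparison of arms is biased. If misoprostol works and placebo women are therefore transfused more often, the bias runs toward no difference.

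**Working it through.** The plan gives no rate, target difference or power for transfusion, so there is no figure of its own to reproduce. The mismatch is one of text, and the numbers below only show its size.

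**Inputs from the documents:** 35 women per arm (Study Summary); transfusion need of up to 20% in abdominal surgery (1.4); planning difference of 0.5 g/dL in hemoglobin (10.2).

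**Assumed inputs:** any transfusion in 20% v 10% (placebo v misoprostol), with 10% v 5% as a lower case for hemoglobin; 30-50% of transfused women transfused only in surgery; net hemoglobin rise of 1-2 g/dL per transfused woman.

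**Women not counted under the literal wording, 20% v 10%**
- All transfused: 35 × (0.20 + 0.10) = 10.5.
- Share of 30%: 10.5 × 0.3 = 3.2. Share of 50%: 10.5 × 0.5 = 5.3. So about 3-5 of 70.

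**Risk difference that the test sees.** Formula: p(placebo) × (1 − share in placebo) − p(misoprostol) × (1 − share in misoprostol). Power is exact two-sided Fisher power at 0.05.

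| Surgery-only share, placebo / misoprostol | Rates counted | Difference | Power |
|---|---|---|---|
| Any transfusion counted | 20% v 10% | 10 points | 12.9% |
| 30% / 30% | 14% v 7% | 7 points | 6.6% |
| 50% / 50% | 10% v 5% | 5 points | 3.0% |
| 50% / 30% | 10% v 7% | 3 points | 1.8% |
| 30% / 50% | 14% v 5% | 9 points | 10.8% |

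The 7-5 point range therefore needs an equal share in both arms. With unequal shares the range is 3-9 points. Power is low in every row. As an example of the precision to expect, 7 v 4 events of 35 give a difference of 8.6 points with a 95% Newcombe interval of −9.0 to 25.9.

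**Hemoglobin bias.** Formula: p(placebo) × rise(placebo) − p(misoprostol) × rise(misoprostol).
- 10% v 5%, equal rise of 1 g/dL: 0.10 × 1 − 0.05 × 1 = 0.05 g/dL. Rise of 2: 0.10 g/dL.
- 20% v 10%, equal rise of 1 g/dL: 0.10 g/dL. Rise of 2: 0.20 g/dL.
- 20% in both arms, rise of 2 (placebo) v 1 (misoprostol): 0.20 × 2 − 0.20 × 1 = 0.20 g/dL.

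Against the planning difference, 0.05/0.5 = 10% and 0.20/0.5 = 40%. On the percent-drop scale, with an assumed baseline of 10-13 g/dL, the range is 0.05/13 = 0.4 to 0.20/10 = 2.0 percentage points.

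**The case against.** The strongest reply is that 10.3 is only loosely worded. Section 1.4 lists conversion to hysterectomy, which happens during surgery, among postoperative complications, next to the transfusion figure itself. The Study Summary assigns Fisher's exact test to categorical variables in general, with no time window, and 2.2.1 already states the full window. This stands as a reason to expect a wording slip. It does not remove the defect, because neither passage defines a transfusion outcome and nothing says that the 10.3 wording includes surgery.

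The data collection sheet is not shown and may well record transfusions in surgery. A recorded field would still leave the analysis wording narrower than the objective, so the point concerns definition and test, not data capture.

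A reader might infer more than the documents support in three ways:
- **That the literal test leaves out the period in which the drug mainly acts.** Section 4.2 says "the duration of pharmacologic action is considered to be only 3 hours", but the dose is given at least one hour before surgery with no upper limit, and no operating time is stated. The overlap cannot be derived. Bleeding in surgery can also lead to a later transfusion, which 10.3 would count.
- **That equal transfusion rates make hemoglobin safe.** That also needs an equal rise per transfused woman, as the last hemoglobin case in the working shows.
- **That the narrower definition costs the trial its power.** At the assumed rates the transfusion comparison has little power to lose.

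**Conclusion.** The point holds for secondary outcomes. The primary outcome, intraoperative blood loss, is not affected. The transfusion analysis as worded does not match objective 2.2.1, probably through loose wording, and the text contains no correction. Percent hemoglobin drop has no rule for transfused women, although the specified draw follows any in-hospital transfusion.

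The sizes are illustrations. They rest on the assumed rates, the assumed share transfused only in surgery and the assumed hemoglobin rise; only the upper figure of 20% and the 35 per arm come from the documents. The 0.05-0.20 g/dL range assumes an equal rise in both arms and is not a bound. No loss of hemoglobin power is claimed, because it depends on which women are transfused. The text mismatch needs none of these assumptions. It should be corrected, and the correction is cheap.

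**What to change.** 1. In 2.4, 10.1 and 10.3, define the outcome as any transfusion from the start of surgery to discharge, to match 2.2.1. Apply the planned Fisher's exact test and report the risk difference with its 95% confidence interval.
2. Keep percent hemoglobin drop as planned. Name pre-operative hemoglobin, already collected under 5.1.8, as a covariate in the adjusted regression. This handles baseline differences but does not correct for transfusion.
3. Pre-specify one sensitivity analysis that accounts for transfusion. One option among several is a Mann-Whitney test that places transfused women at the worst outcome, which is the most negative value under the 10.1 formula.

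**Cost.** Wording in three sections, no extra patients, and a little more analysis. A transfusion field is needed if the data collection sheet lacks one. The rank test gives no estimate in g/dL and must be read as a composite of hemoglobin and transfusion. In 4,000 simulated trials with no hemoglobin effect and 35 per arm, it rejected about 10% of the time at 20% v 10% transfused and about 5-6% at 10% v 5%, against a nominal 5%. None of this changes when a woman is transfused.

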11.0 STUDY MANAGEMENT

11.1 Conflict of Interest

None to disclosure. All investigators will follow the University conflict of interest policy.

11.2 Institutional Review Board (IRB) Approval and Consent

It is expected that the IRB will have the proper representation and function in accordance with federally mandated regulations. The IRB should approve the consent form and protocol.

In obtaining and documenting informed consent, the investigator should comply with the applicable regulatory requirement(s), and should adhere to Good Clinical Practice (GCP) and to ethical principles that have their origin in the Declaration of Helsinki.

Before recruitment and enrollment onto this study, the patient will be given a full explanation of the study and will be given the opportunity to review the consent form. Each consent form must include all the relevant elements currently required by the FDA Regulations and local or state regulations. Once this essential information has been provided to the patient and the investigator is assured that the patient

understands the implications of participating in the study, the patient will be asked to give consent to participate in the study by signing an IRB-approved consent form.

Prior to a patient's participation in the trial, the written informed consent form will be signed and personally dated by the patient and by the person who conducted the informed consent discussion.

Patients who have their pre-op appointment via telehealth calls will also be able to consent as participants using an eConsent form through the secure Northwestern University REDCap. They will be contacted during or after their pre-op appointment by the research coordinator to discuss the study. The research coordinator will consent the patient over the phone and leave time to answer any questions they have about participating in the study before sending the econsent form through REDCap.

11.2 Registration Procedures

N/A.

11.3 Data Management and Monitoring/Auditing

N/A.

11.4 Adherence to the Protocol

Except for an emergency situation in which proper care for the protection, safety, and well-being of the study patient requires alternative treatment, the study shall be conducted exactly as described in the approved protocol.

11.4.1 Emergency Modifications

Investigators may implement a deviation from, or a change of, the protocol to eliminate an immediate hazard(s) to trial subjects without prior IRB approval.

For any such emergency modification implemented, a IRB modification form must be completed within five (5) business days of making the change.

11.4.2 Other Protocol Deviations/Violations

All other planned deviations from the protocol must have prior approval by the Principal Investigator and the IRB. According to the IRB, a protocol deviation is any unplanned variance from an IRB approved protocol that:

- Is generally noted or recognized after it occurs
- Has no substantive effect on the risks to research participants
- Has no substantive effect on the scientific integrity of the research plan or the value of the data collected
- Did not result from willful or knowing misconduct on the part of the investigator(s).

An unplanned protocol variance is considered a violation if the variance:

- Has harmed or increased the risk of harm to one or more research participants.
- Has damaged the scientific integrity of the data collected for the study.
- Results from willful or knowing misconduct on the part of the investigator(s).
- Demonstrates serious or continuing noncompliance with federal regulations, State laws, or University policies.

If a deviation or violation occurs without prior approval from the Principal Investigator, please follow the guidelines below:

11.5 Amendments to the Protocol

Should amendments to the protocol be required, the amendments will be originated and documented by the Principal Investigator. It should also be noted that when an amendment to the protocol substantially alters the study design or the potential risk to the patient, a revised consent form might be required.

The written amendment, and if required the amended consent form, must be sent to the IRB for approval prior to implementation.

11.6 Record Retention

Study documentation includes all Case Report Forms, data correction forms or queries, source documents, Sponsor-Investigator correspondence, monitoring logs/letters, and regulatory documents (e.g., protocol and amendments, IRB correspondence and approval, signed patient consent forms).

Source documents include all recordings of observations or notations of clinical activities and all reports and records necessary for the evaluation and reconstruction of the clinical research study.

Government agency regulations and directives require that the study investigator must retain all study documentation pertaining to the conduct of a clinical trial. In the case of a study with a drug seeking regulatory approval and marketing, these documents shall be retained for at least two years after the last approval of marketing application in an International Conference on Harmonization (ICH) region. In all other cases, study documents should be kept on file until three years after the completion and final study report of this investigational study.

11.7 Obligations of Investigators

The Principal Investigator is responsible for the conduct of the clinical trial at the site in accordance with Title 21 of the Code of Federal Regulations and/or the Declaration of Helsinki. The Principal Investigator is responsible for personally overseeing the treatment of all study patients. The Principal Investigator must assure that all study site personnel, including sub-investigators and other study staff members, adhere to the study protocol and all FDA/GCP/NCI regulations and guidelines regarding clinical trials both during and after study completion.

The Principal Investigator at each institution or site will be responsible for assuring that all the required data will be collected and entered onto the Case Report Forms. Periodically, monitoring visits will be conducted and the Principal Investigator will provide access to his/her original records to permit verification of proper entry of data. At the completion of the study, all case report forms will be reviewed by the Principal Investigator and will require his/her final signature to verify the accuracy of the data.

13.0 APPENDICES

13.1

Data Collection Sheet (see attached)
